7.3.1.2 Potential Risks Associated with Ocrelizumab Use Malignancies, Including Breast Cancer

An increased risk of malignancy with ocrelizumab may exist. Participants should follow standard breast cancer screening guidelines.

Progressive Multifocal Leukoencephalopathy

Progressive multifocal leukoencephalopathy is an important potential risk for ocrelizumab. It has been reported in participants receiving ocrelizumab but only in participants where other contributory factors were present, such as prior immunosuppressive treatment (e.g., natalizumab or fingolimod). Physicians should be vigilant for early signs and symptoms of PML, which can include any new onset or worsening of neurological signs or symptoms, as these can be similar to an MS relapse. If PML is suspected, dosing with ocrelizumab must be withheld. Evaluation of PML, including MRI, confirmatory CSF testing for JCV DNA, and repeat neurological assessments, should be considered. If PML is confirmed, ocrelizumab must be discontinued permanently. More information on PML can be found in Section 7.3.4. Please see the most recent Ocrelizumab Investigator's Brochure for more details regarding PML risk and see Section 7.3.4.1 for guidance on diagnosing PML.

Neutropenia

In the controlled treatment period, decreased neutrophils were observed in 12% and 15% of participants with MS treated with ocrelizumab, in PPMS and RMS, respectively. Most events were mild to moderate in severity. Approximately 1% of the participants had Grade 3 or 4 neutropenia, and no temporal association with infections was identified.

Hypersensitivity Reactions

No hypersensitivity reactions to ocrelizumab were reported in the controlled clinical trials. Hypersensitivity may be difficult to distinguish from IRRs in terms of symptoms. A hypersensitivity reaction may present during any infusion, although not typically during the first infusion. For subsequent infusions, more severe symptoms than previously experienced, or new severe symptoms, should prompt consideration of a potential hypersensitivity reaction. If a hypersensitivity reaction is suspected during an infusion, the infusion must be stopped immediately and permanently. Participants with known IgE-mediated hypersensitivity to ocrelizumab must not be treated.

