Participants who start treatment with commercial ocrelizumab *or another DMT* will discontinue from the study completely and will not enter or continue in the safety follow-up period.

Participants must be withdrawn from treatment (regardless of whether they are in the blinded treatment period or in the OLE phase) under the following circumstances:

- Life-threatening (Common Terminology Criteria for Adverse Events [CTCAE] Grade 4) infusion-related event that occurred during a previous ocrelizumab infusion (see Sections 6.2.2, 7.1.1.3, and 7.3.1)
- Participants who demonstrate active hepatitis B or C infection, either new onset or reactivation in the case of hepatitis B (see Sections 5.13.1.1 and 7.3.1)
- Participants with PML (see Sections 7.3.1 and 7.3.4)
- Participants who decide to discontinue the treatment
- The participant’s Treating Investigator decides that discontinuation of treatment is in the best clinical interest of the participant

It should be noted that upon withdrawal from the study, any untested routine samples will be destroyed. However, information already obtained from samples up until the time of withdrawal will be used.

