6.2.2.1 Handling Infusion-Related Reactions

Handling of IRRs will depend on the intensity of symptoms (see Section 7.1.1.1 for grading of intensity of IRRs).

In the event that a participant experiences a mild to moderate (CTCAE Grade 1 or 2; [Appendix 4](#)) non-allergic infusion-related event, the infusion rate should be reduced to half the rate being given at the time of onset of the event (e.g., from 50 mL/hr to 25 mL/hr or from 100 mL/hr to 50 mL/hr). Once the event has resolved, the investigator should wait for 30 minutes while delivering the infusion at the reduced rate. If tolerated, the infusion rate may then be increased to the next closest rate on the participant's infusion schedule and the rate increments resumed.

Participants who experience a severe infusion-related event (CTCAE Grade 3) or a complex of flushing, fever, and throat pain symptoms, should have their infusion interrupted immediately and should receive aggressive symptomatic treatment. The infusion should be re-started only after all the symptoms have disappeared.

The initial infusion rate at restart should be half of the infusion rate that was in progress at the time of onset of the reaction.

Participants who experience a life-threatening infusion-related event (CTCAE Grade 4) during an infusion should have their infusion immediately stopped and should receive appropriate treatment (including use of resuscitation medications and equipment that must be available and used as clinically indicated). These participants will be withdrawn from treatment and should enter the safety follow-up period (see Section 5.10.1.4).

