6.2.3 Criteria for Re-treatment with Ocrelizumab

Prior to re-treatment with ocrelizumab, participants will be evaluated for the following conditions and laboratory abnormalities. If any of these conditions are present prior to re-dosing, further administration of ocrelizumab should be suspended until resolved or held indefinitely:

- Life-threatening (CTCAE Grade 4) infusion-related event that occurred during a previous ocrelizumab infusion
- Any significant or uncontrolled medical condition or treatment-emergent, clinically significant laboratory abnormality
- Active infection (including active TB infection, either new onset or reactivation)
Participants with active TB infection, either new onset or reactivation, must suspend ocrelizumab treatment for as long as needed to ensure full resolution of the TB infection. These participants should receive medical care in adherence with local/national requirements until complete resolution of the TB infection and should be monitored subsequently as per local medical plans. Upon resolution of the TB infection and based on individual benefit–risk assessments, these participants will have the opportunity to restart ocrelizumab treatment if it is considered beneficial for them. Otherwise, the Treating Investigator can decide to permanently stop ocrelizumab.
- ANC $< 1.5 \times 10^3/\mu\text{L}$
- CD4 cell count $< 250/\mu\text{L}$
- Hypogammaglobulinemia IgG $< 3.3 \text{ g/L}$
- Ongoing pregnancy or breastfeeding (for female participants)

In the event of pregnancy, the investigator must counsel the participant as to the risks of continuing with the pregnancy and the possible effects on the fetus. Given that there are insufficient, well-controlled data from studies testing the use of ocrelizumab in pregnant or breastfeeding women, all infusions of ocrelizumab must be suspended until the completion of pregnancy and breastfeeding. Pregnant and breastfeeding participants should continue to follow the schedule of activities for the OLE; however, no infusions of ocrelizumab will occur. If there is a concern with the ability of a pregnant or breastfeeding participant to perform all scheduled assessments, the investigator must contact the Medical Monitor for further discussion. In the OLE period of the study, restart of ocrelizumab treatment

following pregnancy and breastfeeding will be decided as a result of a thorough benefit/risk discussion between the participant and investigator.

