The substudy protocol was designed because these participants who withdrew early are confounded by a time gap in which they did not receive any treatment at all or received treatment with drugs other than ocrelizumab. Therefore, the data from these participants will need to be analyzed separately from those participants who transitioned directly from the blinded treatment period into the OLE without a gap. As opposed to participants who completed the blinded treatment period and who can transition into OLE directly, the participants who withdrew from blinded treatment early will need to go through a screening step before they are allowed to enter OLE.

SUBSTUDY OBJECTIVES

The same objectives apply to this OLE substudy as for the OLE period described in the main protocol (Section 3).

SUBSTUDY DESIGN

DESCRIPTION OF STUDY PERIODS

This substudy consists of the following study periods: a screening period, an OLE treatment period, and a safety follow-up period.

- Screening period: up to 4 weeks
- OLE treatment period: participants will be receiving open-label ocrelizumab. The same conditions apply to the duration of the OLE phase in this substudy as for the participants entering OLE through the main protocol (Section 4.1).
- Safety follow-up period: the safety follow-up period will begin when the participant completes or discontinues from OLE phase for any reason. The same conditions

Ocrelizumab—F. Hoffmann-La Roche Ltd

162/Protocol WA25046K, Version 11

Appendix 8 Open-Label Extension Substudy in Participants Who Discontinued Treatment in the Blinded Phase of Study WA25046 (cont.)

apply to the duration of the safety follow-up Period in this substudy as for the participants entering OLE through the main protocol (Section 4.1).

END OF SUBSTUDY

The end of the substudy is the same as the end of the main Study WA25046 (protocol Section 4.1.9).

NUMBER OF PARTICIPANTS

Participants who withdrew early from the blinded treatment period of Study WA25046 for any reason are given an option to enter screening for participation in this OLE substudy, except those participants who discontinued due to hypersensitivity to ocrelizumab if it manifested as a Grade 4 infusion-related reaction (IRR). Participants will be allowed to enroll in this substudy up to 24 months after communication from Sponsor.

STUDY POPULATION

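### A Grade 3 infusion reaction with suspected hypersensitivity is stopped for good under Protocol Section 7.3.1.2 but can be restarted under Section 6.2.2.1, and the re-treatment and withdrawal lists omit the bar on known IgE-mediated hypersensitivity

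*Protocol*

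**What the plan says.** Protocol Section 7.3.1.2, under Hypersensitivity Reactions, makes four relevant statements.

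- On recognition: "Hypersensitivity may be difficult to distinguish from IRRs in terms of symptoms".
- On the trigger: "For subsequent infusions, more severe symptoms than previously experienced, or new severe symptoms, should prompt consideration of a potential hypersensitivity reaction".
- On the infusion in progress: "If a hypersensitivity reaction is suspected during an infusion, the infusion must be stopped immediately and permanently".
- On treatment in general: "Participants with known IgE-mediated hypersensitivity to ocrelizumab must not be treated".

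None of the four carries a CTCAE grade.

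Protocol Section 6.2.2.1 manages infusion reactions by grade. Grade 1 or 2 events have the rate halved, and that rule is limited to non-allergic events. Grade 3 events, and a complex of flushing, fever and throat pain, have the infusion interrupted and treated. Then: "The infusion should be re-started only after all the symptoms have disappeared", at half the previous rate. Grade 4 events end treatment.

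The only infusion reaction named in the mandatory withdrawal list of Section 5.6 is: "Life-threatening (Common Terminology Criteria for Adverse Events [CTCAE] Grade 4) infusion-related event that occurred during a previous ocrelizumab infusion". Both pre-dose lists in Section 6.2.3 carry the same Grade 4 item. If any listed condition is present, "further administration of ocrelizumab should be suspended until resolved or held indefinitely". Section 5.4 makes entry to the main OLE depend on meeting the 6.2.3 criteria.

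Appendix 8 lets participants who left blinded treatment early enter an OLE substudy. Its stated exception covers those who stopped for hypersensitivity that took the form of a Grade 4 IRR. It also imports the Section 5.3.1 exclusions and applies Section 7 of the main protocol.

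**The concern.** Two sections appear to give opposite instructions for the same infusion in the same participant. An investigator who suspects hypersensitivity during a severe reaction finds a permanent stop in the warnings section. The section headed as guidance on handling infusion reactions, which is the natural place to look at the bedside, offers a restart at half rate.

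The second issue concerns later doses. The 6.2.3 checklist is what the site works through before dosing. The one explicit bar on treatment in the hypersensitivity text, for known IgE-mediated cases, does not appear on it.

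What is at stake is first participant safety. Second, it is how far the safety tables can be read at face value. SAP Section 4.7.2.1 summarises IRR symptoms that led to modification and to discontinuation of study drug, and SAP Section 4.7.2 summarises adverse events leading to discontinuation. In these cases, the category an event falls into would depend on which protocol section the site followed.

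**Working it through.** No arithmetic applies. The check sets the passages side by side.

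**Step 1. Can both rules reach one event?** Yes. Section 7.3.1.2 ties suspicion to severe symptoms that are new or worse than before at a later infusion, and severe is the label 6.2.2.1 gives to Grade 3. Section 7.3.1.2 itself says symptoms may not separate the two kinds of reaction. Section 7.3.1.1 lists urticaria, dyspnea and laryngeal edema among IRR symptoms. Section 6.4 treats Grade 3 or higher reactions with wheeze or bronchospasm as infusion reactions and sends the reader to 6.2.2 for interruption or discontinuation.

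**Step 2. Does 6.2.2.1 set suspected hypersensitivity aside?** Only at Grade 1–2. The non-allergic qualifier is absent from the Grade 3 paragraph, and the section does not refer to 7.3.1.2. Section 6.2.2 opens by saying that treatment may rarely need to be discontinued and promises guidance, but the only discontinuation that follows is for Grade 4.

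**Step 3. Apply both to an example.** A participant has new severe symptoms, Grade 3, at a later infusion, and the investigator suspects hypersensitivity.

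| Section | Instruction for that infusion |
|---|---|
| 7.3.1.2 | Stop at once and for good |
| 6.2.2.1 | Interrupt, treat, resume at half rate after symptoms clear |

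The two outcomes are incompatible.

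**Step 4. Known IgE-mediated hypersensitivity before a later dose.**

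| Section | Is the condition named? |
|---|---|
| 7.3.1.2 | Yes; treatment is barred |
| 6.2.3, list before re-treatment | No; Grade 4 event and a general item on significant medical conditions |
| 6.2.3, list before the second infusion | No; same two items |
| 5.6, withdrawal list | No; Grade 4 event with a cross-reference that includes 7.3.1, and an investigator-judgment item |
| 5.4, main OLE entry | No; relies on 6.2.3 and does not import 5.3.1 |

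**Step 5. Appendix 8.** Read alone, its exception implies that someone who stopped for hypersensitivity below Grade 4 may enter. The imported 5.3.1 criterion excludes anyone with past severe allergic or anaphylactic reactions to humanized antibodies, and Section 2.1.2 describes ocrelizumab as humanized. That criterion has no Grade 4 threshold. Section 7, including the IgE-mediated bar, also applies to the substudy. The exception therefore suggests a wider door than the other criteria leave open.

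**The case against.** The strongest reply on the infusion in progress is that the sections can be obeyed together. Section 6.2.2.1 concerns infusion-related reactions, and its Grade 3 sentence can be read as a condition on restarting rather than an order to restart. Section 7.3.1.2 is a specific, mandatory instruction that takes over once hypersensitivity is suspected. This is a possible reading, but the text does not state it. Section 6.2.2.1 goes on to set the restart rate. Its authors also drew the allergic distinction for Grade 1–2 and left it out at Grade 3, which invites the opposite reading.

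On later doses, Section 5.6 does cross-refer to 7.3.1, and 5.6 and 6.2.3 contain general items under which a careful investigator could withhold treatment. That stands and softens the omission. It does not put a mandatory bar on the checklist the site uses.

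Three stronger readings are tempting, and the documents do not support them.

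- A reader might infer that 5.6 and 6.2.3 conflict over Grade 4 events, since one withdraws and the other suspends. The 6.2.3 stem covers a mixed list and includes indefinite holding. A past event cannot resolve, so that limb fits withdrawal.
- A reader might infer that Appendix 8 bars only Grade 4 cases. The imported 5.3.1 exclusion and Section 7 both reach further.
- A reader might infer that 7.3.1.2 forbids every later cycle after any suspected reaction. Its permanent stop is attached to the infusion, whereas for PML the same section speaks of discontinuing the drug permanently. Outside known IgE-mediated cases, silence about later cycles is a gap, not a contradiction.

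**Conclusion.** The point holds in two parts. First, the instructions for a Grade 3 reaction with suspected hypersensitivity conflict as written: one section ends the infusion and the other provides for its restart. The example yields two outcomes, not a wider spread, because silence in 5.6 and 6.2.3 is not a further instruction. Second, the bar on treating known IgE-mediated hypersensitivity is missing from both 6.2.3 lists and from the conditions named in 5.6. The Appendix 8 wording is a lesser inconsistency.

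The conclusion rests on the text alone and assumes that an investigator could class one event both as a severe IRR and as suspected hypersensitivity, which 7.3.1.2 itself allows for. No frequency can be derived. Section 7.3.1.2 says no hypersensitivity reactions were reported in the controlled trials, which also means that Appendix 8, open only to people who left blinded treatment, may have no one to whom its exception applies. The likely effect on any safety table is correspondingly small. The primary efficacy method does not depend on it. It should be corrected because a single case could be serious and the repair is cheap.

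**What to change.** The sponsor should reconcile Sections 7.3.1.2 and 6.2.2.1, and state in 6.2.2.1 whether the Grade 3 restart text applies when hypersensitivity is suspected, with a cross-reference between the two. Sections 5.6, both lists in 6.2.3 and the Appendix 8 eligibility wording should then be made consistent with 7.3.1.2, including its separate treatment of suspected and known IgE-mediated hypersensitivity. Appendix 8 should read consistently with the 5.3.1 exclusion it imports. Which clinical rule applies is for the sponsor's safety physicians, and none is proposed here.

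The cost is wording in one protocol amendment. Depending on the rule chosen, a very small number of participants might be handled differently. No change to sample size or to the efficacy analyses follows.

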7.3.2 Corticosteroids

The adverse reactions of corticosteroids may result from unwanted glucocorticoid actions or from inhibition of the hypothalamic-adrenal axis. Please refer to the local Prescribing Information.

7.3.3 Antihistamines

The adverse reactions depend on the sedating properties of the antihistamine and include, but are not limited to, nausea, drowsiness, headaches, dry mouth, and allergic reactions such as rash. Please refer to local Prescribing Information (OCREVUS USPI).

7.3.4 Progressive Multifocal Leukoencephalopathy

Progressive multifocal leukoencephalopathy is a potentially fatal neurological condition linked to reactivation of a polyomavirus (JCV) and active viral replication in the brain. Polyomavirus infection is acquired in childhood and up to 80% of adults demonstrate serological evidence of past infection. Reactivation of JCV replication with transient viremia or viriuria unassociated with clinical symptoms may occur spontaneously in healthy persons. Less frequently, CNS symptoms associated with active viral replication in brain tissue is observed. The clinical syndrome is significantly more frequent among immune suppressed participants.

Physicians should consider the diagnosis of PML in any participant presenting with new neurological deficits localized to the cerebral cortex, such as cortical symptoms/signs, behavioral and neuropsychological alteration, retrochiasmal visual defects, hemiparesis, cerebellar symptoms/signs (e.g., gait abnormalities, limb incoordination), at each visit.

If PML is considered, a neurological consultation should be obtained and treatment suspended until PML has been ruled out. If PML is confirmed in a participant receiving ocrelizumab, no further infusions should be administered and the participant will be withdrawn from treatment (see Section 5.6). No known interventions can reliably prevent PML or adequately treat PML, if it occurs.

It is not known whether the risk of PML is altered by anti-CD20 treatment given as monotherapy. See Section 7.3.4.1 for guidance on the diagnosis of PML.

Progressive multifocal leukoencephalopathy should be reported as a serious adverse event (with all available information) with immediate notification of the Medical Monitor. Study drug should be withheld and participants with confirmed PML should be withdrawn from the study.

There is no known treatment or cure for PML. Treatment considerations are discussed in the medical literature (Calabrese et al. 2007).

Detailed information regarding PML risk with ocrelizumab treatment can be found in the current Ocrelizumab Investigator's Brochure.

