^c After the first infusion, an evaluation will be performed before each subsequent infusion to ensure that the participant remains eligible for re-treatment (see Section 6.2.3).

^d Trial participants entering the study early will undergo more than 5 treatment cycles. When applicable, subsequent dosing cycles will consist of the same dosing regimen at 24-week intervals as Cycles 2–5.

^e The OLE phase for eligible participants begins after the primary database lock at the completion of the blinded treatment period. The OLE phase can terminate at any moment or cycle (see Section 4.1.9).

^f During the OLE phase, all participants will receive dual infusions of ocrelizumab 300 mg × 2 for the first cycle. For the subsequent cycles, participants will continue open-label treatment with a single infusion of 600 mg ocrelizumab IV every 24 weeks. For participants randomized to the ocrelizumab group, the first infusion of ocrelizumab in the OLE phase should respect a minimum of 20 weeks from last infusion in the blinded treatment period. For participants randomized to the placebo group, the first infusion of ocrelizumab in the OLE phase can occur once a participant meets the re-treatment criteria (see Section 6.2.3) at a scheduled visit following communication with the Sponsor.

Table 5 Overview of the Study Design and Dosing Regimen (cont.)

- ^g The safety follow-up period starts after the last 24-week treatment cycle has been completed (either during the blinded treatment period or the OLE phase). Participants who withdraw from treatment will also enter the safety follow-up period. The safety follow-up period will last *up to* 48 weeks following the last infusion. *Participants who start treatment with commercial ocrelizumab or another DMT will discontinue from the study completely and will not enter the safety follow-up period.*
- ^h A dose of 100 mg methylprednisolone IV and oral or IV antihistamine, such as diphenhydramine 50 mg or equivalent dose of alternative, will be administered prior to ocrelizumab or placebo infusions. In participants where methylprednisolone is contraindicated, equivalent doses of other IV steroids (e.g., dexamethasone) should be used as premedication.

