5.10.1.4 Visits During the Safety Follow-Up Period

Participants who discontinue treatment for any reason (including, but not limited to, withdrawal from blinded treatment, withdrawal from OLE phase, or Sponsor decision to terminate the study) will be followed up for *up to* 48 weeks after the last infusion in the safety follow-up period with visits every 12 weeks.

Participants should be encouraged to complete the safety follow-up period.

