5.10.1.6 Withdrawal Visits During the Blinded Treatment Period

At the moment a participant meets 1 or more of the withdrawal criteria ([Section 5.6](#)), that particular participant is regarded withdrawn from treatment. Efforts should be made to complete the respective schedule of activities as soon as possible, if necessary at an extra visit which completes the withdrawal visit.

At the termination of the study (see [Section 4.1.9](#)), the participants will discontinue ocrelizumab treatment and should move into the safety follow-up period or will receive commercial ocrelizumab (if available in that country). All participants will undergo a

complete final evaluation according to the Withdrawal from Treatment Visit in [Table 4](#). Thereafter, all participants will be treated according to individual center practice.

Participants who withdraw from the blinded treatment period will complete all assessments as shown in [Table 2](#) and will enter the safety follow-up period. Participants withdrawing from the OLE phase will complete all assessments as shown in [Table 4](#) and will enter the safety follow-up period.

For participants who have withdrawn from the blinded treatment period or the OLE phase or who are not eligible for treatment with ocrelizumab, it is at the discretion of the investigator to decide on further treatment of the underlying disease.

However, since sufficient data are not available to inform risks associated with switching to other products, certain treatments for MS, such as lymphocyte-depleting agents or lymphocyte-trafficking blockers (e.g., alemtuzumab, natalizumab, fingolimod, dimethyl fumarate, cyclophosphamide, azathioprine, etc.), are strongly discouraged for as long as the participant remains B cell depleted because of unknown effects on the immune system (e.g., increased risk, incidence, or severity of infection; see [Section 5.5.2](#) for recommendations on alternative treatments for MS and [Section 5.23.5](#) for prolongation of safety monitoring period for participants on alternative MS treatments).

Despite all efforts, participants may withdraw from the study during the safety follow-up period. Participants withdrawing from the safety follow-up period will undergo the assessments shown in [Table 3](#).

Note: at the Withdrawal from blinded treatment period Visit, an MRI scan will be required only if not performed in the previous 4 weeks.

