5.12.4 Neurological Examination

A neurological examination will be performed at every planned and unscheduled visit. See Section 5.11.1.1.

In the presence of newly identified or worsening neurological symptoms at any given time in the study (blinded treatment period, safety follow-up period, or OLE phase), a neurological evaluation should be scheduled promptly. The Treating Investigator should assess whether the participant is experiencing:

- A relapse of MS or MS worsening. In this case, the Treating Investigator should request EDSS to be performed by the Examining Investigator (see Section 5.11.1).
- Another neurological (non-MS) disorder. In this case, an adverse event should be reported.

Study investigators will screen participants for signs and symptoms of PML by evaluating neurological deficits localized to the cerebral cortex, such as cortical symptoms/signs, behavioral and neuropsychological alteration, retrochiasmal visual defects, hemiparesis, cerebellar symptoms/signs (e.g., gait abnormalities, limb incoordination).

A brain MRI scan and CSF analysis may be warranted to assist in the diagnosis of PML. See Section 7.3.4.1 for guidance on the diagnosis of PML.

Participants with suspected PML, defined as a new or worsening neurological symptom which necessitates MRI and or lumbar puncture and CSF analyses to rule out PML, should be withheld from study treatment until PML is ruled out by complete clinical evaluation and appropriate diagnostic testing (see Section 7.3.4.1). The medical responsible and Medical Monitor should be contacted by e-mail. In addition, the medical responsible should be immediately contacted by phone.

A participant with confirmed PML should be withdrawn from the study. Progressive multifocal leukoencephalopathy should be reported as a serious adverse event (with all available information) with immediate notification of the Medical Monitor (see Sections 7.2.2 and 7.2.3).

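### For confirmed PML the protocol gives two conflicting instructions: leave the study, or stop treatment and enter safety follow-up

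*Protocol*

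**What the plan says.** Two places in the protocol call for withdrawal from the study:

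- Section 5.12.4: "A participant with confirmed PML should be withdrawn from the study".
- Section 7.3.4, fifth paragraph: "participants with confirmed PML should be withdrawn from the study".

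Three places call only for stopping treatment:

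- Section 5.6 opens its mandatory list with "Participants must be withdrawn from treatment (regardless of whether they are in the blinded treatment period or in the OLE phase" and includes the item "Participants with PML (see Sections 7.3.1 and 7.3.4".
- Section 7.3.4, third paragraph: on confirmation, "no further infusions should be administered and the participant will be withdrawn from treatment (see Section 5.6".
- Section 7.3.1.2 requires permanent discontinuation of ocrelizumab and does not mention leaving the study.

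Sections 4.1.4 and 5.6 both state that withdrawal from treatment and withdrawal from the study must be kept apart. Table 5, footnote g, gives the consequence of the first: "Participants who withdraw from treatment will also enter the safety follow-up period". Section 5.10.1.4 sets that follow-up at up to "48 weeks after the last infusion in the safety follow-up period with visits every 12 weeks". For the second, Table 3 (footnote b) provides one Withdrawal from Study visit, in the column marked as the end of observation.

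**The concern.** Section 7.3.4 assigns two statuses to the same event, two paragraphs apart, and each status leads to a different schedule. A site that acts on Section 5.12.4 or on the later paragraph of 7.3.4 would close the participant out with one visit. A site that acts on Section 5.6 would keep the participant in safety follow-up.

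PML is described as potentially fatal, and a participant treated with ocrelizumab would still be B-cell depleted. Section 4.1.5.6 gives the safety of B-cell repletion as a reason for the follow-up period. At stake are:

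- the remaining scheduled safety visits and the telephone interviews between them;
- the collection window for unrelated serious events and for non-serious events, which Section 7.2.2.1 ties to the end of safety follow-up;
- the recorded disposition, because SAP Section 4.3 summarises time to treatment discontinuation, time to study discontinuation and entry into safety follow-up separately.

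Section 5.6 also says that untested routine samples are destroyed on study withdrawal, while Section 7.3.4.1 stores the extra PML plasma and urine with the routine JCV samples. Whether the destruction rule reaches those samples is arguable, but only the study-withdrawal reading raises the question.

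**Working it through.** **Can the texts be read together?** Leaving the study includes stopping treatment, so the instructions agree on dosing. They disagree on what follows: one route continues observation and the other ends it. No sentence about PML says which prevails.

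**Which was meant?** The evidence favours safety follow-up. Section 5.6 says must; Section 5.12.4 and the later paragraph of 7.3.4 say should. Section 5.10.1.6 states that once a Section 5.6 criterion is met, "that particular participant is regarded withdrawn from treatment", and sends participants who withdraw from blinded or open-label treatment into follow-up. Section 5.23.4 does the same for the open-label phase. None of these makes an exception for PML.

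**What does the literal reading cost?** The plan gives no figure, so this is counted from Table 3.

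- Scheduled visits: weeks 12, 24, 36 and 48 after the last infusion.
- Immunoglobulins (Ig): weeks 24 and 48, and at the Withdrawal from Study visit.
- Telephone interviews: every 4 weeks between visits, taken as 2 per 12-week interval (weeks 4 and 8 of each).
- Let t be the weeks from last infusion to PML confirmation. Assume t is 0 to 24 (24-week cycles on schedule, the 2-week gap between paired infusions ignored). Any Withdrawal from Treatment visit is taken to be the same under both readings.

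Net loss of visits or Ig = remaining scheduled − 1, because the Withdrawal from Study visit supplies one of each. Interviews lost = 2 × remaining 12-week intervals. Reporting window lost = 48 − t weeks.

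| t (weeks) | Visits left | Net visits lost | Ig left | Net Ig lost | Interviews lost | Window lost (weeks) |
|---|---|---|---|---|---|---|
| 0 | 4 | 4 − 1 = 3 | 2 | 2 − 1 = 1 | 2 × 4 = 8 | 48 − 0 = 48 |
| 12 (after that visit) | 3 | 3 − 1 = 2 | 2 | 2 − 1 = 1 | 2 × 3 = 6 | 48 − 12 = 36 |
| 24 | 2 | 2 − 1 = 1 | 1 | 1 − 1 = 0 | 2 × 2 = 4 | 48 − 24 = 24 |

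Table 3 footnotes c and d restrict the week 12 and week 24 visits by the timing of withdrawal. Applied strictly:

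- t = 0: visits at weeks 12, 36 and 48, so 3 − 1 = 2 visits and 1 − 1 = 0 Ig lost.
- t = 12: visits at weeks 24, 36 and 48, so 3 − 1 = 2 visits and 2 − 1 = 1 Ig lost.
- t = 24: visits at weeks 36 and 48, so 2 − 1 = 1 visit and 1 − 1 = 0 Ig lost.

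The net loss per case is therefore 1 to 3 visits (1 to 2 if the footnotes are strict) and 0 to 1 immunoglobulin assessments. It is smaller if dosing was delayed or the participant was already in follow-up.

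**The case against.** The strongest counter-argument is that this is loose wording with an obvious meaning. Section 5.13.1.1 says participants who develop hepatitis B or C are withdrawn from the study and then directs them into safety follow-up. Hepatitis sits beside PML on the Section 5.6 list, so for a sibling criterion study plainly stands for treatment. With the general rule in Section 5.10.1.6, a careful reader reaches the right answer. That stands as evidence of intent. It does not remove the conflict: the hepatitis sentence supplies the follow-up instruction and the PML sentences do not, and the protocol itself warns against merging the two terms.

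The second argument is that little would be lost. This also largely stands:

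- The closing visit collects EDSS, neurological examination, FACS, safety laboratory tests and immunoglobulins.
- The Medical Monitor is notified at once (Sections 5.12.4 and 7.3.4).
- Adverse events are followed (Sections 5.6 and 7.1.2), and related serious events are reportable without time limit (Section 7.2.2.1).
- The documents give no PML rate for this trial. Section 7.3.1.2 describes PML with ocrelizumab only alongside other contributory factors, such as earlier natalizumab or fingolimod, which Section 5.3.3 excludes at entry to the blinded period.

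A third argument is that efficacy was not fully considered. Under Scenario C of SAP Table 2, a participant with an initial progression who stops treatment and has no confirmatory EDSS counts as confirmed, so lost follow-up visits could in principle change the status of a single case. Given how rare PML would be, this cannot bear on the primary conclusion; SAP Section 2.3 lists the primary analysis as completed, with a cutoff of 24 July 2015.

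**Conclusion.** The concern holds. Section 5.12.4 and the fifth paragraph of Section 7.3.4 contradict Section 5.6 and the third paragraph of Section 7.3.4, and the two study-withdrawal sentences are wrong as written. Severity is minor. The loss range above rests on confirmation within 24 weeks of the last infusion and on a site following the study-withdrawal sentences literally. The interview count also assumes two calls per interval. No sample size, power or alpha figure is involved. The reason to correct it is that sites need one instruction for a potentially fatal event in a B-cell-depleted participant.

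**What to change.** In Section 5.12.4 and the fifth paragraph of Section 7.3.4, replace withdrawal from the study with withdrawal from treatment followed by entry into the safety follow-up period. Section 6.2.2.1 already uses that formula for life-threatening (Grade 4) infusion-related events. Both sentences would then agree with Sections 5.6, 5.10.1.4, 5.10.1.6 and 5.23.4 and with Table 5, footnote g.

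The cost is two sentences of protocol text, with no new visits or assessments. The hepatitis sentence in Section 5.13.1.1 could be tidied at the same time for consistency; it is not needed to resolve the PML conflict, because it already directs participants to follow-up.
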